## **Study Design**

This study will be a prospective, non-randomized, open-label study of Omegaven™ with a total enrollment of 100 patients, for provision of parenteral lipid calories. The study cohort, receiving the PN at 1g/kg/day, will be compared to historical controls at UNMC where parenteral lipid calories were provided exclusively through soybean-based formulations, as well as, assessing the study cohorts need for small bowel and liver transplantation.

### **A. Basic Design Characteristics**

The study will include 4 periods, as described below.

#### **1. Screening**

Prior to the Evaluation Period, appropriate documentation will be obtained to determine which patients may qualify for the study.

#### **2. Evaluation**

During this period, the Investigator will evaluate to confirm eligibility. All these procedures are performed at initial evaluation on all patients in the Intestinal Rehabilitation Program, regardless of entry into a study. In addition to a review of body systems, the baseline evaluations will include the recording of body weight and routine urine and blood laboratory analyses. These blood and urine analyses will determine vitamin, trace element, essential fatty acid levels, serum electrolytes, hydration status, kidney function and liver function. Patients will also have radiology and GI exams. It is possible the evaluation may include a liver biopsy. The patient's pre-study TPN prescription will also be recorded.

#### **3. Treatment**

The Treatment Period will not begin until the patient undergoes a full initial evaluation. Informed consent will be obtained before treatment is initiated. After the initial evaluation is complete and inclusion criteria are found to be met, therapy with Omegaven™ will be initiated at the goal dose of 1 gram per kilogram per day, over 12-24 hours. Omegaven™ will be infused intravenously through either a central or peripheral catheter alone or in conjunction with parenteral nutrition. If additional fat calories are needed, they will be provided via the central route. The same standards of care provided to all patients receiving parenteral nutrition solution will be followed, with routine nutritional monitoring.

In the event that a patient is unable to achieve adequate calories parenterally and is unable to tolerate enteral feeds, it may be necessary to evaluate whether or not the patient should continue the study with Omegaven™ or resume therapy with the conventional fat

emulsions so that additional parenteral fat calories can be given. The clinical team will determine if the patient should be removed from the protocol, and the IRB and FDA will be notified.

Orders for Omegaven™ will contain the following data elements;

- Total daily dose to administered in mL
- The hourly infusion rate (total daily dose ÷ the number of hours to be infused)

Prior to the administration of each Omegaven™ dose, two nurses will check the dose dispensed against the physician's orders and verify that the infusion pump settings (hourly rate, volume to be infused) are correct before the infusion is started.

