### Efficacy and Safety Variables

The efficacy and safety variables in this study will be the change from the baseline assessment to the end of follow-up assessment or end of treatment assessment for the variables listed below. The variables will be determined from: the measurement of body weight, the recording of TPN prescriptions, blood and urine analyses, radiology reports, GI exams, and possible liver biopsies.

- Parenteral Nutrient Requirements (determined from the TPN/PN prescription)
  - TPN/PN infusions (days/week)
  - TPN/PN fluid volume (cc/week)
  - TPN calories (kcal/week)
  - TPN protein (g/week)
  - TPN lipid (g/week)
  - Intravenous vitamins (type and # of infusions/week)
  - Intravenous trace elements (type and # of infusions/week)
  
- Assessment of Nutritional Status
  - Body Composition
  - Body Weight
  
  - Nutrient and Metabolic Profile (Blood analyses)
  - Vitamins- A, B12, C, D, E, folate
  - Minerals and trace elements - calcium, phosphorus, iron, selenium, zinc
  - Serum Proteins - total protein, albumin, globulin
  - Lipid profile - essential fatty acids levels
  - Citrulline, D-lactic acid
  - Serum Electrolytes – (sodium, potassium, chloride, bicarbonate, magnesium)
  
- Assessment of Hydration Status/ Renal Function (Blood analyses)
  - Blood urea nitrogen
  - Serum creatinine

- Assessment of Liver Function (Blood analyses)  
Total bilirubin, direct and indirect bilirubin, alkaline phosphatase, SGOT, SGPT, LDH.
- Assessment of Upper and Lower GI tract/Liver  
Upper and Lower endoscopy, mucosal biopsies and bacterial cultures  
Ultrasound of abdomen/Small bowel follow through, Barium enema  
Liver biopsy (based on clinical indication)

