### **Discontinuation of Therapy**

Patients will continue to be followed by the UNMC Intestinal Rehabilitation Program upon discontinuation of therapy with Omegaven™ until they are completely free of any rehabilitation needs and are tolerating a full diet by mouth.

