## **Patient Discontinuation**

The Investigators may discontinue an individual patient from the study at any time. They may voluntarily withdraw at any time. A patient may experience Dose Modification, Disruption of Therapy, or Discontinuation of Therapy from the study for the following medical or administrative reasons.

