### **Discontinuation of Therapy –**

- In the event that a patient is unable to achieve adequate calories parenterally and is unable to tolerate enteral feeds, it may be necessary to evaluate whether or not the patient should continue the study with Omegaven™ as monotherapy or resume therapy with conventional fat emulsions so that additional parenteral fat calories can be given.
- Adverse Event (AE) – Any patient with anaphylactic or allergic reactions to Omegaven™ will not continue treatment and will be withdrawn from the protocol.
- Inter-current Illness – If a patient develops an illness during the course of the study that is not associated with the condition under study and that requires treatment inconsistent with the protocol requirements (such as an interruption of regular participation in the study), the patient may be discontinued from further participation in the study. A patient may also be discontinued from the study if he develops an inter-current illness or complication that in any way justifies his withdrawal from the study. However, if an inter-current illness develops which can be managed without significant interference with the requirements of the protocol, the patient need not be discontinued.
- The patient will complete treatment with Omegaven™ in this study when he/she is completely off PN, develops a contraindication for further use, or the patient/family requests to be removed from the study.

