## Statistical Analysis

Data from the two sets of patient population will be pooled and compared (i.e., current protocol patients prescribed Omegaven™ PN compared to historical controls where parenteral lipid calories were provided exclusively through soybean-based formulations). Potential for effect in different patient populations will be minimized by matching patients enrolled in the Omegaven™ protocol to historical controls. Frequency matching will be utilized given the difficulty of paired matching in this patient population. Specific matching criteria will include gender, age, etiology of short bowel syndrome, and severity of liver disease (parenteral nutrition- associated liver disease).

Continuous data will be expressed as mean +/- SEM. A two-way repeated measure ANOVA will be used to compare differences in the two groups with respect to changes between the Evaluation assessment and the subsequent analyses performed at Treatment and Treatment/Follow-up Assessments. Incidence of adverse events in each treatment arm will be compared using Fisher's exact test. Univariate and multivariate analysis will be used to identify baseline factors that may influence outcome. A P-value <0.05 will be considered statistically significant.

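### Open-label clinicians can take Omegaven patients out of the study, and no text keeps those patients' later transplants as study outcomes

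*Combined protocol and SAP*

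**What the plan says.** The Objectives section makes need for small bowel transplantation the primary question, with historical controls as comparator. Study Design describes a non-randomized, open-label study of 100 patients.

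Omegaven patients can leave in these ways:

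- **Treatment (Study Design A.3).** If parenteral calories are inadequate and enteral feeds are also not tolerated: "The clinical team will determine if the patient should be removed from the protocol". The same sentence requires notice to the IRB and FDA.
- **Patient Discontinuation, opening paragraph.** "The Investigators may discontinue an individual patient from the study at any time". No criterion is given. Patients may also withdraw voluntarily.
- **Patient Discontinuation, Discontinuation of Therapy.** An exit is allowed for an "inter-current illness or complication that in any way justifies his withdrawal from the study". Patients with an allergic reaction "will not continue treatment and will be withdrawn from the protocol"; that exit is mandatory.

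On what happens next, the earlier Discontinuation of Therapy section says: "Patients will continue to be followed by the UNMC Intestinal Rehabilitation Program upon discontinuation of therapy". The Treatment/Follow-up Period section sends patients who go home back to their referring physician.

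On who is analysed, Statistical Analysis refers to "current protocol patients prescribed Omegaven™ PN compared to historical controls", and Study Design speaks of "assessing the study cohorts need for small bowel and liver transplantation". The Efficacy and Safety Variables section measures change "from the baseline assessment to the end of follow-up assessment or end of treatment assessment", but transplantation is not among its listed variables. The Statistical Analysis section defines no analysis set and no rule for withdrawals or censoring.

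**The concern.** The exits are worded as leaving the protocol or the study, not merely as stopping a drug. Clinicians who know the treatment decide most of them. The exit in the Treatment section is triggered by failure of both feeding routes. Such patients plausibly have above-average risk of needing a small bowel transplant; that is an inference, not a statement in the documents.

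The controls were already exclusively on soybean lipid, so an exit back to conventional emulsion has no counterpart among them. The documents do not describe how controls with a similar course were selected or followed.

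If removed patients are left out, or stay in the denominator while their later transplants go unrecorded, the Omegaven transplant rate can change without any drug effect. Two analysts could each follow the text faithfully, use different populations, and report different primary results.

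**Working it through.** The documents give no removal rate, transplant rate, number of controls or power calculation, so there is no plan figure to reproduce. The only documented input is the 100 Omegaven patients. With 100 in the denominator, each uncounted transplant lowers the Omegaven rate by 1/100 = 1 percentage point.

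**Assumed inputs.** No drug effect; *r* = share removed, 5–15%; *k* = their transplant risk relative to the Omegaven group average, 0.5–2.

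**Case A: removed patients are excluded.** Apparent rate ÷ true rate = (1 − rk)/(1 − r), so the relative reduction is r(k − 1)/(1 − r).

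**Case B: removed patients stay in the denominator and a share *m* of their later transplants is missed.** Relative reduction = m·r·k. The table takes m = 1, complete loss.

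| r | k | A: relative reduction | B with m = 1: relative reduction |
|---|---|---|---|
| 0.05 | 0.5 | 0.05 × (−0.5)/0.95 = −2.6% (an increase) | 2.5% |
| 0.10 | 1 | 0 | 10% |
| 0.10 | 2 | 0.10/0.90 = 11.1% | 20% |
| 0.15 | 0.5 | 0.15 × (−0.5)/0.85 = −8.8% (an increase) | 7.5% |
| 0.15 | 2 | 0.15/0.85 = 17.6% | 30% |

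Case A has no fixed sign and is zero at average risk. Case B favours Omegaven whenever any transplant is missed.

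**In absolute terms**, with an assumed true rate of 30% and r = 0.10, Case A gives:

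- k = 2: 0.30 × 0.80/0.90 = 26.7%
- k = 1: 30.0%
- k = 0.5: 0.30 × 0.95/0.90 = 31.7%

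**Effect on false positives.** Two-proportion z-test, nominal two-sided 5%, true rate 30% in both groups, an assumed 100 controls, r = 0.10:

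| Scenario | Apparent Omegaven rate | Two-sided type I error |
|---|---|---|
| A, k = 0.5 | 31.7% | 5.7% |
| A, k = 1 | 30.0% | 5.0% |
| A, k = 2 | 26.7% | 8.0% |
| B, k = 2, 25% missed | 0.30 × (1 − 0.05) = 28.5% | 5.6% |
| B, k = 2, 50% missed | 0.30 × (1 − 0.10) = 27.0% | 7.6% |
| B, k = 2, 100% missed | 0.30 × (1 − 0.20) = 24.0% | about 16% |

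If every dosed patient and every later transplant is counted, the apparent rate equals the true rate and the error stays at 5% under these assumptions.

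**The case against.** The strongest defence is that the all-treated reading is the natural one. Statistical Analysis refers to patients prescribed Omegaven, Study Design to the study cohort, and the Inclusion Criteria to the first 100 eligible patients. No sentence says removed patients leave the analysis. A reader might infer from the removal wording that the plan excludes them; the documents do not say so, and that reading should not be attributed to the plan.

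Later transplants would also often be known. The Background section places the program alongside small bowel transplantation in one comprehensive service at the same centre, and program follow-up continues after therapy stops. The protocol does not cleanly separate stopping therapy from leaving the study: allergic and illness-related exits sit under a Discontinuation of Therapy heading. Removal for inadequate calories needs two conditions together and is notified to the IRB and FDA, so it is not silent.

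Most of this stands, and it makes complete loss of later transplants unlikely. It does not close the gap. Continued program follow-up is clinical care, not a rule that later transplants are study outcomes. Wording about removal or withdrawal from the protocol or study pulls against the all-treated reading. Return to referring physicians means some outcomes may not reach the investigators unless requested. Notifying regulators does not settle the analysis.

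**Conclusion.** The point holds as a gap in the primary comparison that should be closed. The exits end study participation, largely at open-label clinical discretion, with no counterpart rule for controls, and no text secures the later transplants. Taken literally, they permit selective loss in the Omegaven group only.

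The size cannot be derived from the documents. Over the assumed ranges, exclusion moves the apparent rate by anything from about a 9% relative increase to an 18% relative reduction. Missed transplants give a 2.5–30% relative reduction if all are missed, and proportionately less otherwise.

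Two stronger readings are not supported. One is that the bias must favour Omegaven: under exclusion that requires removed patients to have above-average risk, which is plausible but undocumented. The other is that a 30% reduction, or a type I error near 16%, is the expected size: both are extremes that assume complete loss of later transplants.

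**What to change.** 1. In Treatment (Study Design A.3), and in the opening paragraph and Discontinuation of Therapy part of Patient Discontinuation, replace removal from the protocol or study with: *taken off Omegaven, with transplant outcome follow-up continued, unless the patient or family withdraws consent*.
2. Add to Statistical Analysis: *Every patient who receives at least one dose of Omegaven is analysed in the Omegaven group for small bowel transplantation, and later transplants are counted whatever the later lipid product or reason for stopping.*
3. Report the number taken off Omegaven, by reason, with their transplant outcomes.

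Any start point and follow-up window must be defined the same way in both groups. Starting Omegaven patients at first dose but controls at first eligibility should be avoided. A transplant between eligibility and first dose would count for a control but could never appear among dosed patients, and this immortal-time bias would favour Omegaven.

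The cost is a few sentences, one recorded item (reason for stopping), and some outcome requests to outside physicians. Patients who return to soybean lipid may dilute a true effect. If they gain no benefit, an assumed 30% relative reduction becomes 0.30 × (1 − rk): 29.3% at r = 0.05, k = 0.5, and 21.0% at r = 0.15, k = 2. Dilution could also mask harm, which is one reason to report those taken off Omegaven separately.

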#### **4. Treatment/Follow-up Period**

During the follow-up period, patients will continue to be followed by the Intestinal Rehabilitation Program per our standard care for any patient on PN: All patients in IRP are followed with regular blood work, including CBC/diff and CMP at least weekly initially, and in most cases 2-3 times per week. Based on clinical progress, the frequency of laboratory evaluation may be reduced, but is rarely less than once weekly until patients are stable and off PN. These procedures and tests would continue to be performed.

In addition to standard nutritional monitoring, essential fatty acids and serum triglycerides levels will be sent monthly. If a patient should experience lipid intolerance, then serum lipid profiles, including triglycerides, will be sent weekly for the first 4 weeks of therapy, and if stable will be reduced to every two weeks. This monitoring is additional to what would be standard in this population. Any adverse experiences will be recorded for every patient throughout the entire enrollment of the study.

Patients will remain on Omegaven™ until weaned from PN and may continue monotherapy with Omegaven™ as an additional source of calories after the dextrose/protein portion of PN is discontinued.

Upon returning home, patients will be returned to the care of the physician who referred them for participation in the study. Arrangements will be made with the patient's primary care physician to continue usual follow-up. Patients will initially be seen by their primary care physician within one week of returning home.

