## ABSTRACT

In the United States, patients dependent upon parenteral nutrition (PN) receive parenteral fat emulsions composed of soybean oils. Lipids are necessary in PN-dependent patients due to their high caloric value and essential fatty acid content. They have been implicated in predisposing patients to PN-associated liver disease, and children requiring prolonged courses of PN are at risk for developing PN-associated liver disease. Animal studies have shown that IV fat emulsions such as fish oil that are high in eicosapentaenic and docosahexaenoic acid reduce impairment of bile flow which is seen in cholestasis caused by conventional fat emulsions. We hypothesize that a fat emulsion comprised of omega-3 fatty acids (i.e., fish oil) such as Omegaven™ will be well tolerated and will reduce the inflammatory effect in the liver of prolonged PN exposure, with the potential of reversing any hepatic dysfunction due to PN/IFE use. By administering Omegaven™ in place of conventional phytosterol/soybean fat emulsions we may reverse or prevent the progression of PN associated cholestasis and thus allow the patient to be maintained on PN until they are able to ingest adequate nutrition enterally.

All patients in the Intestinal Rehabilitation Program at UNMC with an abnormal serum bilirubin (>2mg/dL), receiving PN and not meeting an exclusion criteria will be approached for enrollment. Upon enrollment, the PN lipid source will be switched to Omegaven, and patients will continue to be followed in standard fashion for ongoing intestinal rehabilitation. Patients will continue to have regular follow-up including laboratory evaluation at least once weekly, with periodic radiologic and endoscopic evaluation as per our standard of care. As hypertriglyceridemia is a possible side effect of Omegaven, weekly triglyceride levels will be added to regular labs. Patients will be continued on Omegaven until weaned from intravenous lipids per standard of care. Clinical data will be collected prospectively and will be compared with historical controls.

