### **Monitoring and Possible Dose Reductions**

In addition to standard nutritional monitoring, essential fatty acids will be sent monthly and serum triglyceride levels will be sent weekly. If lipid intolerance develops, defined as serum triglyceride levels > 200 mg/dL, the following will be considered prior to reducing the dose:

- a) If the level was obtained while the patient was receiving a continuous 24- hour infusion of Omegaven™, the total dose will be infused over 20 hours, and a repeat serum triglyceride level obtained prior to resuming the infusion 4 hours later.
- b) Other sources of lipid intolerance will be considered and addressed (drugs, renal disease)

If the triglycerides continue to remain high despite the aforementioned interventions, a dosage reduction of 25% of the current dose will be considered.

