### **Dose Modification for Lipid Intolerance -**

- If lipid intolerance develops, defined as serum triglyceride levels > 200 mg/dL, all sources of lipid intolerance should be considered and addressed (drugs, renal disease, etc). If the triglycerides continue to remain high despite the aforementioned interventions, a dosage reduction of the current dose will be considered.

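### Routine triglyceride testing on Omegaven is monthly in one section and weekly in two others, and the monthly section's step-up to weekly depends on the test it spaces out

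*Combined protocol and SAP*

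**What the plan says.** Three places in the combined protocol and SAP set a routine triglyceride frequency.

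- **Abstract:** "As hypertriglyceridemia is a possible side effect of Omegaven, weekly triglyceride levels will be added to regular labs".
- **4. Treatment/Follow-up Period:** "essential fatty acids and serum triglycerides levels will be sent monthly". The same paragraph adds a conditional rule: "If a patient should experience lipid intolerance, then serum lipid profiles, including triglycerides, will be sent weekly for the first 4 weeks of therapy", with a reduction to every two weeks if stable.
- **Monitoring and Possible Dose Reductions:** "essential fatty acids will be sent monthly and serum triglyceride levels will be sent weekly".

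Lipid intolerance is defined twice, both times by one threshold. Monitoring and Possible Dose Reductions has "If lipid intolerance develops, defined as serum triglyceride levels > 200 mg/dL, the following will be considered prior to reducing the dose"; Dose Modification for Lipid Intolerance has "If lipid intolerance develops, defined as serum triglyceride levels > 200 mg/dL, all sources of lipid intolerance should be considered and addressed".

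The assessment lists also mention triglycerides. Treatment Period and Extended Outpatient Treatment Period include them among chemistries from which the investigator may choose any or all, at least weekly in the first and once a week in the second. Treatment/Follow-up Assessments refers back to the Evaluation list, where the lipid entry names only essential fatty acids.

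**The concern.** All three statements are current text, and they cannot all be followed as written. The Abstract gives hypertriglyceridemia as the reason for adding weekly levels. A result above 200 mg/dL starts the steps under Monitoring and Possible Dose Reductions: for a level drawn during a 24-hour infusion, shorten the infusion to 20 hours and repeat the test; look for other causes; and, if levels stay high, consider cutting the dose by 25%. Staff who work from the Treatment/Follow-up section can start those steps later than staff who work from the dosing section.

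The conditional rule does not protect against this. Weekly testing begins only once intolerance is known, and intolerance is known only from a triglyceride result. The rule is also tied to the start of therapy, so intolerance found later has no clear schedule.

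**Working it through.** **Can the sections be reconciled?**

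| Possible reading | What the text shows |
|---|---|
| Weekly during treatment, monthly during follow-up | The Treatment/Follow-up section sets a rule for the opening weeks of therapy and keeps patients on Omegaven "until weaned from PN and may continue monotherapy with" it afterwards. Neither the Abstract nor the dosing section limits weekly testing to a phase. |
| Standard weekly bloods already cover triglycerides | The Treatment/Follow-up section names CBC/diff and CMP as the regular blood work and describes the lipid monitoring as extra to standard care. |
| The assessment lists decide | The two treatment lists are discretionary, and the Evaluation list names only essential fatty acids. |

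None of these readings removes the conflict.

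**Scheduled tests.** In the first 4 weeks there are 4 required triglyceride tests under the weekly rule and about 1 under the monthly rule. The first monthly result therefore arrives at about the time the 4-week window of the conditional rule closes.

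**Delay to detection.** The plan states no figure to reproduce. Assume that the rise above 200 mg/dL is sustained, that its onset is uniform between required tests, and that tests are drawn on schedule. Then mean delay = interval / 2:

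- weekly: 7/2 = 3.5 days;
- monthly: 28/2 = 14, 30/2 = 15, 31/2 = 15.5 days.

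The longest delay is the interval itself: 7 days against about 30.

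**Allowing for discretionary tests.** Take a 28-day cycle with the required test on day 28. Suppose tests on days 7, 14 and 21 are each drawn with probability p, and let q = 1 − p. Every onset waits 3.5 days on average to the next possible test day. The expected number of further weeks is q + q² + q³ for onset in week 1, q + q² in week 2, q in week 3 and 0 in week 4. Averaging over the four weeks gives

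mean delay = 3.5 + 7(3q + 2q² + q³)/4.

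| p (assumed) | q | 3q + 2q² + q³ | Mean delay (days) |
|---|---|---|---|
| 0 | 1 | 6 | 14.0 |
| 0.25 | 0.75 | 3.797 | 10.1 |
| 0.50 | 0.50 | 2.125 | 7.2 |
| 0.75 | 0.25 | 0.891 | 5.1 |
| 1 | 0 | 0 | 3.5 |

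The documents give no value for p, so the table shows a range and does not estimate practice at the site.

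**Extra assays per patient-year, weekly against monthly.** 365/7 − 365/28 = 39.1; 365/7 − 365/30 = 40.0; 365/7 − 365/31 = 40.4.

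**The case against.** The strongest reply is that the practical gap is smaller than 30 days against 7. Triglycerides are on both active-treatment chemistry lists, blood work is said to be done 2 to 3 times a week in most cases, and staff applying the dose rule would be reading the section that already says weekly. This stands as a limit on size: the monthly-rule delays are upper bounds. It does not settle the required frequency, because the lists are optional.

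A period split is also arguable. Treatment and Treatment/Follow-up are numbered as separate periods, and the weekly rule sits among dosing instructions that open with the treatment period. The reference to early therapy in the monthly section, and the absence of any phase limit on the weekly rule, count decisively against it.

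The step-up point could be called unremarkable, since any rule that tests more often after an abnormal result depends on the earlier test, and a monthly result can still trigger it. That is fair. It is a consequence of the frequency conflict and not a separate defect, but it does show that the conditional rule cannot make up for monthly testing.

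Finally, the documents give neither the incidence of levels above 200 mg/dL nor the harm from a delay of days to weeks, and the responses to a high level are only to be considered. The delay figures therefore measure lateness, not clinical consequence.

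**Conclusion.** The conflict is real and should be fixed. The same patients on the same drug have two required triglyceride schedules, and nothing in the documents says which prevails. The maximum gap between required tests is about 30 days against 7. Mean detection delay is about 15 days (14 to 15.5) against 3.5, if a rise is sustained and its onset uniform; discretionary weekly testing would bring the first figure down towards the second. The contradiction itself rests on the text alone and needs none of these assumptions. It concerns safety monitoring and the timing of the dose-reduction rule. No effect on the need for small bowel transplantation, the sample size or the error rate has been shown.

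**What to change.** In 4. Treatment/Follow-up Period, require essential fatty acids monthly and triglycerides weekly for as long as the patient is on Omegaven. Weekly is the frequency in two of the three statements and the only one given a safety reason; the sponsor should confirm that it is what was intended. Replace the conditional intolerance rule in that section with a reference to the steps under Monitoring and Possible Dose Reductions. The every-two-weeks step-down has to go with it, because it would fall below the routine weekly frequency. As optional tidying, mark triglycerides as required weekly in the Treatment Period and Extended Outpatient Treatment Period lists.

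The cost is a wording amendment and no additional patients. Against the monthly rule alone it means about 40 more assays per patient-year (39 to 40 depending on month length); against the Abstract and the dosing section it adds none. Laboratory frequency "is rarely less than once weekly until patients are stable and off PN", so most assays can use blood already drawn, at the price of the assay and a slightly larger sample. The exception is Omegaven monotherapy after the rest of PN has stopped. Weekly draws are not assured there, so some patients, including children, may need extra ones. The existing weekly rule already implies that burden.
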